## 2.0 Analysis (A) Primary analysis: As randomized (Aims 1 and 2).

**AIM 1:** To compare the effectiveness in increasing receipt of the second dose of influenza vaccine of personalized text message reminders with embedded influenza vaccine health-literacy-promoting information versus usual care in a diverse pediatric population in need of two doses in a given influenza season.

**AIM 2:** To compare the effectiveness in improving the timeliness of the second dose of influenza vaccine of personalized text message reminders with embedded influenza vaccine health-literacy-promoting information versus usual care in a diverse pediatric population in need of two doses in a given influenza season.

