#### **2.3.1 Time zero**

Time zero for all time to event analyses is the date of child's initial vaccine dose.

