### 2.4.2 Time to event outcomes – variation across sites

We will use the same approach for time to vaccination, with mixed effects models and letting site be a random effect. In other words, we allow estimated time to vaccination vary by site, and test whether this variation is significant.

Statistical significance of the random site effect can be tested using likelihood ratio statistics.

Stata: mestreg –

```
mestreg treat covariates || site:, distribution(weibull) int(12)
```

```
predict resite, reffects
```

In this example, the variable "resite" will contain the value for the "prediction" at the site level. The prediction will then represent the site-level time to event, and by ordering the sites by this value, we can determine which sites fared best and which fared worst.

R: coxme

Alternative but similar approaches are now in R (Therneau 2018) for the Cox model

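### SAP section 2.4.2 reads the predicted site random effect as a time and ranks practices on it; it is a deviation on the model's linear predictor, and on a hazard scale larger values mean an earlier second dose

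*Combined protocol and SAP*

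**What the plan says.** SAP section 2.4 is labelled tertiary and descriptive. Within it, section 2.4.2 addresses time to vaccination with site as a random effect.

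- The Stata command, up to its closing bracket, is "mestreg treat covariates || site:, distribution(weibull) int(12". It has a random intercept for site, and no option requests a time (accelerated failure time) metric.
- The site values come from "predict resite, reffects".
- They are interpreted as follows: "The prediction will then represent the site-level time to event, and by ordering the sites by this value". The purpose of the ordering is to identify the practices at the two extremes, best and worst.
- A second route through R's coxme is then offered: "Alternative but similar approaches are now in R (Therneau 2018) for the Cox model".

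The section does not name the metric of the Weibull fit, give the sign convention, or say which end of the ordering is the good one.

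**The concern.** A predicted random effect is not on the scale of the outcome. It says how far a site's linear predictor lies from that of the average site. If the linear predictor is a log hazard, and the event is a desirable one, a high value marks a fast practice. A reader who takes the SAP at its word and treats the value as a time would take a high value to mark a slow one.

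The ranking is the stated purpose of the step. Section 2.4.1.1 also plans to describe the sites at the extremes and approach them about barriers. Section 2.4.2 says that it follows the same approach. If the follow-up were carried over and the list were upside down, the enquiry about barriers would go to the quickest practices.

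**Working it through.** The documents give no figure on this point, so there is none to reproduce. The check is of scale and direction.

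**Inputs from the SAP**

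- Time origin (2.3.1): "Time zero for all time to event analyses is the date of child's initial vaccine dose". The event is the second dose.
- Good direction (Aim 2, section 2.0): "To compare the effectiveness in improving the timeliness of the second dose of influenza vaccine". Earlier is better.
- Ranked quantity (2.4.2): the predicted site random intercept, written u below.

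**Step 1: hazard scale.** In both a Cox mixed model and a Weibull model in the hazard metric, h(t|u) = h0(t) × exp(xb + u). At fixed covariates, with S0 the probability of still awaiting the second dose at an average site, uptake by time t is 1 − S0(t)^exp(u). This rises with u. For a Weibull with shape a, the median time is [ln 2 / exp(xb + u)]^(1/a). The time ratio against an average site is therefore exp(−u/a), which falls as u rises.

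**Step 2: numbers for uptake.** Assume, since the documents do not give it, 50% uptake by day 90 at an average practice.

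| u | exp(u) | Uptake by day 90 |
|---|---|---|
| +0.3 | 1.35 | 1 − 0.5^1.35 = 0.608 |
| −0.3 | 0.741 | 1 − 0.5^0.741 = 0.402 |

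Read as times, +0.3 exceeds −0.3, so the practice with 61% uptake looks slower than the one with 40%.

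**Step 3: numbers for time.** Assume shape a = 1.3.

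| u | Hazard ratio exp(u) | Time ratio exp(−u/1.3) |
|---|---|---|
| +0.4 | 1.49 | 0.735 (sooner) |
| −0.4 | 0.67 | 1.36 (later) |

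**Step 4: time scale.** In the accelerated failure time form, log T = xb + u + error, so the time ratio is exp(u) and rises with u. A larger value then means a later dose, and ordering by u agrees with ordering by time. The value is still a deviation in log time, not a number of days.

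**Step 5: simulation on the hazard scale.** A random-intercept Weibull model was fitted with 12-point quadrature to 15 simulated data sets. There were 45 sites, within the protocol's 40 to 50. The other main settings were assumed: 45 children per site, shape 1.3, and a between-site SD of 0.2, 0.4 or 0.6 on the log-hazard scale, with five data sets for each SD.

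- Predicted site effects lay between about −1.2 and +1.5 and centred near zero.
- Their Spearman correlation with the model-predicted site median time was −1.00 in every data set.
- Their correlation with the true site median time was −0.56 to −0.95.
- Their correlation with the site's observed second-dose proportion was +0.92 to +0.99.
- The five sites with the largest effects were always the five with the shortest predicted times.

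The −1.00 follows from the hazard-scale assumption and says nothing about which metric the SAP's command uses. The simulation does show what the saved values look like: small positive and negative numbers, not times.

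**The case against.** A reader might infer that the SAP's plan will certainly swap the best and worst practices. The case against that is strong on three counts.

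1. **No sort direction is given.** The SAP says that sites will be ordered and the extremes identified, not that low values are good. An analyst who knows the scale could order them correctly.
2. **The disputed sentence describes the Weibull output.** The Cox route appears afterwards as an alternative, and nothing says its random effect will be read as a time. Calling the two routes similar makes the transfer plausible but does not state it.
3. **The Weibull metric is not stated.** The command requests no time metric, but the documents do not say which metric applies when none is requested. Some of the text leans towards time: 2.4.2 speaks of estimated times differing by site, and 2.3 sets out to avoid Cox regression and hazard ratios. On a time-scale fit nothing is reversed.

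It can also be said that negative values would alert anyone expecting days, and that the site contact in 2.4.1.1 is written for random treatment slopes in the binary model, whereas 2.4.2 has only a random intercept.

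All of this stands against a certain reversal. None of it rescues the interpretation itself. Under either metric and either model, the predicted random effect is a deviation on the linear predictor, and the SAP says that it represents a time.

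**Conclusion.** The interpretation in section 2.4.2 is wrong as written, whatever metric is used. Its effect on the ranking is conditional:

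- **Hazard-scale fit** (Cox by construction, or the Weibull command if fitted in the hazard metric): reading the value as a time, with shorter better, reverses the order completely.
- **Time-metric fit:** the order is right, but the value is a log-time deviation.

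The documents do not support saying that the list will be reversed, because they fix neither the Weibull metric nor the sort direction. The 61% versus 40% contrast illustrates the mechanism under assumed uptake and assumed site effects; it is not an estimate for this trial.

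The reach is small. The analysis is tertiary and descriptive, and no Aim 1 or Aim 2 treatment estimate depends on it. What could go wrong is the description of individual practices, and any contact with them that relied on this ranking.

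**What to change.** Replace the interpretive sentence in section 2.4.2 with:

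> The predicted random effect is each site's deviation from the average site on the scale of the fitted model. On a hazard scale, larger values mean an earlier second dose; on a time scale, larger values mean a later one. Sites will be ordered on the model-predicted second-dose uptake at day 42 or day 90 (or RMST), with higher uptake (or shorter RMST) meaning better.

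The predictions should use the same treatment arm and covariate values for every site, so that the order reflects the site effect alone. Days 42 and 90 are already horizons in sections 2.3.4 and 2.3.5.1. The wording is valid for a Weibull model in either metric and for the Cox alternative, so the choice of model need not be settled first. The cost is a short text change and one extra prediction step, with no new data and no change to any other analysis.

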### **3.0 AIM 3:** To assess parental and child characteristics that modify text message effectiveness

The goal for this Aim is to identify subgroups for which the intervention was either particularly effective or not effective. All subgroups should be pre-specified (see candidates below). They should also be few, owing to issues of multiple comparisons. For that reason, all confidence bounds of subgroup estimates will be adjusted so that bounds correspond to Bonferroni corrections for multiple contrasts. This aim is exploratory.

#### **3.0.1 Candidate effect modifiers**

The following factors represent the original candidate effect modifiers.

##### **3.0.1.1 Available for all children**

- child age-group (6-23 months; 2-8 years)
- child gender (male; female)
- child health insurance (public/uninsured; commercial (including Tricare)). This variable is used as a partial indicator of socioeconomic status.
- seasonality of the initial dose (early influenza season, mid-season, late season)

##### **3.0.1.2 Available for all caregivers**

- text language (English; Spanish)

##### **3.0.1.2 Available for all practice sites**

- appointment scheduling for the 2nd dose (walk-in; appointment)
- primary practice setting/urbanicity (urban, inner city; urban, not inner city; suburban; rural). Practice setting is self-reported and the categories align with the Periodic Survey from the American Academy of Pediatrics.

##### **3.0.1.3 Available for only questionnaire respondents**

###### ***Caregiver:***

- age

- highest education level
- relationship to a child
- receipt of previous text message reminders from their practice site/doctor
- type of text message plan
- text messaging frequency
- overall childhood vaccine hesitancy
- flu shot safety
- perceived risk of getting sick from the flu

*child:*

- reported health status
- race/ethnicity (including sub-group)

The first challenge is to try to identify potential subgroups based on groups of these individual factors without making the error of estimating each candidate factor one by one and then looking for “interaction” of treatment by factor.

### 3.0.2 Effect modification on the additive scale

We define effect modification on the additive scale for the effects of treatment on outcome. For binary outcomes, effect modification therefore means that the effect of treatment is in terms of “percentage points” of improvement, and effect modification is present if improvement (in terms of percentage points) from the intervention differs by the effect modifier grouping.

### 3.0.3 Latent class analysis of patient-level factors - exploratory analysis

Latent class analysis can reduce many patient level factors into a single dimension factor. (Lanza 2013). With our candidate factors distilled into a categorical latent class, we propose to simplify the process of identifying and reporting potential effect modification. These analyses will be exploratory

## 3.1 Subgroup analyses – binary outcomes – primary analysis

We will pre-specify subgroups of interest based on combinations of patient characteristics. Risk differences, rather than relative risks, will be the scale on which to estimate treatment\*subgroup interactions, so that final results we can report in terms of percentage points of improvement.

### 3.1.1 Estimating within site effects of subgroups

The within-site effect modification estimate represents the difference in treatment effects across levels of the effect modifier contrasted within (rather than across) sites. For this estimate we shall first use a linear fixed effects model, as implemented in Stata command “*xtreg,fe*”, assuming that the outcome will lie in the probability range of 0.2 and 0.8.

This approach will be a first estimate to be followed by the decomposition approach in section 3.1.2.

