### **3.1.2 Parametric subgroup analysis – decomposing the within and across site effects**

We assume that absolute rates (risks) of second vaccine will not lie at the ends of the interval [0,1]. If that is the case, then we can estimate risk differences with subgroups and then across subgroups in the following 3-step process.

**Step 1:** Using a generalized linear effects, create a site-level variable that equals the mean rate of the group at the site. If at one site, for example, 20% of the children have a chronic medical condition, then create a factor =0.2 for that site (called group\_bar).

**Step 2:** Specify a generalized linear model with the following covariates where treatment and group are 0/1 factors:

Treatment + group + treatment\*group + group\_bar + treatment\*group\_bar + covariates.

This model will decompose the within-site effect of treatment by group and the across-site effect of treatment by group.

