### **3.2 Subgroup analysis – time-to-event – secondary**

The goal is to identify subgroups of patients who responded well (or not at all) to the intervention in terms accelerating the time to completing of the vaccination series. Contrasts between groups will be estimated and reported as

Restricted mean survival time analyses can be done with interactions (treatment\*subgroup).

Effect modification will be estimated on the difference scale.

Using pseudo-observation approach:

Stata: `glm pseudo treat##subgroup, vce(cluster site)`

Results can be standardized for covariates (see above).

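### SAP 3.1.1 labels the site-fixed-effects treatment-by-group interaction as the within-site estimate; it is a marginal contrast that mixes within- and across-site modification, and the within-site estimate comes from 3.1.2 (minor, Aim 3 only)

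*Combined protocol and SAP*

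**What the plan says.** Section 3.1 of the SAP sets the scale for the binary subgroup analyses: "Risk differences, rather than relative risks, will be the scale on which to estimate" the treatment-by-subgroup interactions. Section 3.1.1 defines the target as a difference in treatment effects "contrasted within (rather than across) sites". It then names the estimator: "For this estimate we shall first use a linear fixed effects model", in Stata xtreg,fe. It gives no covariate list and closes with "This approach will be a first estimate to be followed by the decomposition approach in section 3.1.2".

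Section 3.1.2 describes its method "in the following 3-step process", of which two steps appear in the text. Step 1 is to "create a site-level variable that equals the mean rate of the group at the site" (group_bar). Step 2 fits treatment, group, treatment\*group, group_bar, treatment\*group_bar and covariates. The section concludes: "This model will decompose the within-site effect of treatment by group and the across-site effect of treatment by group". It states no variance estimator.

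Four other places bear on the point. Section 2.4 anticipates that the intervention effect may differ between practices. Section 3.2, on time to event, clusters by site in its command "glm pseudo treat##subgroup, vce(cluster site)". Section 3.0 calls Aim 3 exploratory and applies Bonferroni corrections to all subgroup confidence bounds. The protocol's section on parent randomization allocates 1:1 within each site.

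**The concern.** The estimand in 3.1.1 is a within-site contrast, but the estimator assigned to it does not isolate one. Because allocation is 1:1 inside every site, treatment varies within sites, and so does the product of treatment and the site's group prevalence. Site intercepts therefore cannot absorb that product. If practices with many children in a group respond differently from practices with few, that difference enters the treatment\*group coefficient.

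What is at stake is interpretation. Under its present label, a difference between practices could be read as a difference between types of children in the same practice, or a real within-practice difference could look smaller than it is. Sections 3.1.1 and 3.1.2 could also give two different within-site figures, and the SAP does not say outright which one counts.

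**Working it through.** **1. Which model is meant.** The covariate list in 3.1.1 is a reading: treatment + group + treatment\*group with site intercepts. Two things support it. Section 3.1 names the treatment-by-subgroup interaction as the quantity to estimate, and group_bar is first created in 3.1.2.

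**2. What that model estimates.** Let the treatment effect for a child with group indicator G at a site with prevalence p be

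effect = constant + within × G + d × p.

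Here d is the treatment\*group_bar coefficient, that is, the total across-site slope minus the within-site slope. With 1:1 allocation in every site, the interaction is the slope of the treatment effect on G over all children:

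interaction = within + d × Cov(p, G)/Var(G) = within + w × d,

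where w = Var(p)/Var(G) is the between-site share of the modifier's variance. Equivalently, it is (1 − w) × within-site slope + w × total across-site slope. It equals the within-site contrast only if w = 0 or d = 0. For a binary G, this slope is the marginal difference in effect between the two groups.

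**3. Size.** The plan gives no figure to reproduce. Inputs from the protocol are up to 4,000 parents, two seasons and 40-50 practices. With 45 practices this gives 4,000/2/45 ≈ 44 children per site and season. The assumed control rate of 46% lies within the background's 40-60%. Also assumed are a mean effect of 8 points, site intercept SD of 8 points, mean group prevalence 0.5, and the values of w and d. The simulation used 1,500 replicates.

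The standard error of the interaction is about 4 × 0.5/√1,980 = 0.045, or 4.5 points (simulated 4.46-4.47). With bias b, an interval misses the within-site value with probability

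Φ(b/SE − z) + Φ(−b/SE − z),

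where z = 1.96 for 95% intervals. For the Bonferroni bounds of section 3.0, z = 2.576 if there are 5 contrasts. Five is an assumption, one for each child or caregiver factor available for everyone; the SAP gives no number.

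True within-site modification 0, one season; entries are for d = 10 / 20 / 30 points:

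| w | w × d | simulated interaction (points) | 95% interval misses | Bonferroni (5) misses |
|---|---|---|---|---|
| 0.05 | 0.5 / 1.0 / 1.5 | 0.49 / 1.09 / 1.29 | 5 / 6 / 6% | 1.0 / 1.2 / 1.3% |
| 0.1 | 1.0 / 2.0 / 3.0 | 1.13 / 1.84 / 3.11 | 6 / 7 / 11% | 1.2 / 1.7 / 3.1% |
| 0.2 | 2.0 / 4.0 / 6.0 | 2.20 / 4.16 / 5.91 | 8 / 15 / 26% | 2.0 / 5.0 / 10.5% |
| 0.3 | 3.0 / 6.0 / 9.0 | 3.02 / 6.06 / 9.00 | 10 / 27 / 52% | 2.9 / 11.2 / 28.8% |

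The nominal miss rates are 5% and 1%. As an example, at w = 0.2 and d = 30, b/SE = 5.91/4.47 = 1.322. The adjusted miss rate is Φ(1.322 − 2.576) plus a negligible second term, or 10.5%.

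- **3.1.2 model:** the treatment\*group term stayed within 0.2 points of 0 in the same runs.
- **Marginal reading:** the true marginal differences were 0.5-1.5, 1.0-2.9, 2.0-5.9 and 3.0-8.8 points at the four values of w, so 3.1.1 tracks the marginal contrast.
- **Opposite signs (within 10, d = −20):** 3.1.1 gave 9.0, 8.1, 5.8 and 4.0 points; 3.1.2 gave 9.8-10.1.
- **d = 0:** 3.1.1 gave 10.0-10.2 when the truth was 10, so there was no bias.
- **Both seasons combined (standard error 3.2), within 0, d = 20:** the bias is unchanged. The 95% intervals missed in 6%, 9%, 24% and 49% of runs. The formula with b = 20w and z = 2.576 gives about 1.4%, 2.6%, 9% and 24%.
- **Clustering is no cure for this bias:** in a run with 40 children per site, d = 20 and a 27% between-site share, tests of the 3.1.1 interaction rejected in 19.3% of runs with model-based errors and 18.0% with clustered errors.

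**4. Across-site term of 3.1.2.** With no modification and site treatment effects varying with an assumed SD of 5, 10 or 15 points, nominal 5% tests of treatment\*group_bar rejected in 6%, 8-10% and 13-15% of runs with model-based errors. With site-clustered errors the rate was 5-6%. The within-site term stayed at 4-6% either way.

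**The case against.** The strongest reply is that the SAP already handles this. Section 3.1.1 calls its result a first estimate and sends the reader to 3.1.2, whose model recovers the within-site value. That stands, and it reduces the point to a wrong label on a preliminary step plus an unstated order of precedence. A reader might infer that the SAP has no valid within-site estimate; it has one, in 3.1.2.

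It can also be said that 3.1.1 writes out no model, so treatment-by-site terms are not excluded. That is true, and if they were intended, saying so would settle the matter.

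A reader might take the 52% in the table as the error of the planned intervals. The documents do not support that, because section 3.0 adjusts all subgroup bounds; with 5 contrasts the figure is 29%. The adjustment widens intervals without removing bias, so the adjusted rates still exceed their nominal 1% where w is large. That corner is also demanding: at w = 0.3 and d = 30, the SD of site prevalence is √(0.3 × 0.25) = 0.27. Group composition alone would then give site effects an SD of about 8 points, as large as the assumed mean effect.

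On variance, a reader might infer that 3.1.2 prescribes model-based standard errors. It prescribes none, and one of its three announced steps is not in the text. The remark on clustering is therefore conditional. Section 3.2 claims no within-site contrast and is not at fault.

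**Conclusion.** The point holds as a mislabelled estimator. On the natural reading of 3.1.1, the xtreg,fe interaction is a marginal subgroup contrast that mixes within- and across-site modification; it is not the within-site estimate the section defines. The error is w × d. It is small for w up to 0.1 (at most 3.1 points for d up to 30, against a standard error of 4.5) and material only when the modifier's prevalence differs strongly between practices. The documents give neither w nor d, so the sizes are conditional on the assumed ranges.

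The secondary point, on the text as available, is that a model-based interval for the across-site term of 3.1.2 would be too narrow if treatment effects vary by site, as section 2.4 anticipates. The within-site term is unaffected.

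Severity is minor. Aim 3 is exploratory, the right model is already in the SAP, and the analyses of Aims 1 and 2 do not depend on this.

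**What to change.** In 3.1.1, state that the within-site estimate is the treatment\*group coefficient of the 3.1.2 model, and relabel the xtreg,fe result as a marginal subgroup contrast that mixes within- and across-site modification. This takes one sentence and costs no precision.

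Alternatively, add treatment\*group_bar to the 3.1.1 model. The standard error of the interaction then rises from 4.47 to 4.64 (4%) at w = 0.05, to 4.77 (7%) at w = 0.1 and to 5.06 (13%) at w = 0.2, and from 4.46 to 5.41 (21%) at w = 0.3. Treatment-by-site terms cost about the same.

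In 3.1.2, if the across-site term is to be reported, state vce(cluster site), as 3.2 already does. If site effects do not in fact vary, this moves the error for that term only from about 5% to 5-6%. No new data are needed, and 3.2 needs no change.

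### The linear fixed-effects model for binary subgroup effects (SAP 3.1.1) names no robust variance, so subgroup bounds can be somewhat too narrow or too wide; minor, and almost free to fix

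*Combined protocol and SAP*

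**What the plan says.** SAP 3.1, headed "Subgroup analyses – binary outcomes – primary analysis", estimates treatment-by-subgroup effects as risk differences. Section 3.1.1 gives the first model for the within-site contrast: "For this estimate we shall first use a linear fixed effects model, as implemented in Stata command" `xtreg, fe`, "assuming that the outcome will lie in the probability range of 0.2 and 0.8". It then gives the status of that model: "This approach will be a first estimate to be followed by the decomposition approach in section 3.1.2".

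Section 3.1.2 continues: "Specify a generalized linear model with the following covariates where treatment and group are 0/1 factors". It states no family, link or variance estimator. Neither section mentions robust or clustered standard errors.

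The secondary, time-to-event subgroup analysis in 3.2 does specify one: "glm pseudo treat##subgroup, vce(cluster site)".

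For multiplicity, 3.0 says that "all confidence bounds of subgroup estimates will be adjusted so that bounds correspond to Bonferroni corrections for multiple contrasts", without giving the number of contrasts. The same paragraph adds: "This aim is exploratory".

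**The concern.** A linear model of a 0/1 outcome has unequal residual variance by construction, because a child with completion probability p contributes p(1-p). Without a variance option, the named command estimates one residual variance and uses it for every subgroup. A small subgroup then receives a standard error driven mainly by the variance of the large one.

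The 0.2 to 0.8 condition in 3.1.1 supports the linear form of the mean. It does not equalise the variance, since p(1-p) still runs from 0.16 to 0.25 over that range.

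The SAP introduction makes point estimates and confidence bounds the main form of reporting, so Aim 3 will be read from such bounds. If a minority subgroup sits near 50% and the majority near 80% or 20%, the minority's bounds are too narrow and an apparent difference is too easily found. In the opposite configuration they are too wide and a real difference may be missed. The direction depends on which subgroup is smaller and on its rate, so a reader cannot allow for it by eye. None of this requires the text-message effect to vary between children or sites.

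**Working it through.** The documents give no standard error, power or coverage figure for the subgroup analyses, so there is nothing to reproduce. The check compares the pooled-variance standard error with the true one.

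**Inputs from the documents.** Outcome probability 0.2 to 0.8 (SAP 3.1.1); background second-dose completion 40 to 60% (protocol Background); 1:1 allocation (Parent randomization); up to 4,000 parents over two seasons (Overview).

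**Assumptions.** Base level two-sided 95%; the subgroup shares and subgroup-specific rates used below; 1, 7 or 18 contrasts. Seven counts the modifiers listed as available for all children, caregivers or sites; 18 adds the 11 questionnaire items. The ratios below do not depend on total sample size.

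**Formulas.** Let s be the minority share, and v_min and v_maj the mean p(1-p) in each subgroup over the two arms. Pooled variance: v = s·v_min + (1-s)·v_maj.

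- Minority risk difference, stated/true SE = sqrt(v / v_min).
- Interaction, stated/true SE = sqrt{ v·[1/s + 1/(1-s)] / [v_min/s + v_maj/(1-s)] }.
- Miss rate = 2·[1 - Φ(z × ratio)].

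**Limit within the SAP's range.** All variances lie between 0.16 and 0.25, so the ratio lies between sqrt(0.16/0.25) = 0.80 and sqrt(0.25/0.16) = 1.25.

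**At 40 to 60% completion.** Variances lie between 0.24 and 0.25, so the ratio lies between sqrt(0.24/0.25) = 0.98 and sqrt(0.25/0.24) = 1.02. Coverage of the 95% interaction interval is then 94.6 to 95.4% for minority shares of 10 to 50%.

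**Illustration: s = 0.20, constant 6-point effect.** Minority 0.47 control and 0.53 treated; majority 0.74 and 0.80 (mean 0.77).

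- v_min = 0.47 × 0.53 = 0.2491.
- v_maj = (0.1924 + 0.1600)/2 = 0.1762.
- v = 0.2 × 0.2491 + 0.8 × 0.1762 = 0.1908.
- Minority ratio = sqrt(0.1908/0.2491) = 0.875, that is, about 12% too small; miss rate 8.6%.
- Interaction ratio = sqrt(0.1908 × 6.25 / (1.2455 + 0.2203)) = 0.902; miss rate 7.7%.

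With the rates reversed, v = 0.2345. The minority ratio is sqrt(0.2345/0.1762) = 1.15 (15% too large). The interaction ratio is 1.11, with a miss rate of 3.0%. Simulating the interaction in this scenario gave 7.7%, and 2.5% reversed, against 4.7 to 5.0% with heteroskedasticity-robust errors.

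**Edge of the range, s = 0.10.** Minority 50% and majority 20%: interaction ratio 0.84, coverage 89.9%. Minority 20% and majority 50%: ratio 1.19, coverage 98.1%.

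**Equal-sized subgroups.** With s = 0.5 the interaction ratio is exactly 1, whatever the two rates. The subgroup-specific risk differences can still be off: at 50% and 80%, v = 0.205, giving sqrt(0.205/0.25) = 0.91 and sqrt(0.205/0.16) = 1.13.

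**Bonferroni.** It changes z, not the ratio. In the 0.84 case:

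| Contrasts | Nominal miss | Actual miss | Relative | Shortfall, points |
|---|---|---|---|---|
| 1 | 5% | 10.1% | 2.0 | 5.1 |
| 7 | 0.71% | 2.43% | 3.4 | 1.7 |
| 18 | 0.28% | 1.22% | 4.4 | 0.9 |

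**Effect of a robust variance.** Simulated site fixed-effects model, 45 sites × 44 children (about half of 4,000), 5-point effect, 10% minority, 3,000 runs; coverage of the 95% interaction interval:

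| Minority / majority rate | Conventional | Heteroskedasticity-robust | Site-clustered |
|---|---|---|---|
| 50% / 25% | 92.0% | 94.2% | 93.4% |
| 25% / 50% | 97.0% | 95.4% | 94.6% |

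With rates of 40% and 50%, in either order, all three gave 94.3 to 95.3%.

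**The case against.** The strongest reply is that the SAP never says its reported bounds come from this model. Section 3.1.1 calls it a first estimate that 3.1.2 will follow, and gives a command name rather than full code. A reader might infer that the primary subgroup analysis takes its error bars from equal-variance standard errors. The documents do not support that: conventional errors are inferred from silence and the command's default, and no section says which model supplies the bounds. This stands. It does not close the gap, because 3.1.2 leaves its own family and variance open and so cannot be assumed to repair the problem.

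Second, the only completion rate in the documents is 40 to 60%, where the error is about 2% or less. The rates and shares in the illustration are not documented. That also stands, so the bounds can be wrong rather than are wrong. However, 40 to 60% is background completion overall, not the spread across insurance, age or language groups, and the SAP itself allows for 0.2 to 0.8.

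Third, a reader might infer that the Bonferroni adjustment magnifies the error. Only the relative miss rate grows; the standard-error ratio is unchanged and the absolute shortfall shrinks. Eighteen contrasts is also a high count: 3.0 wants few subgroups, 3.0.1 warns against testing factors one by one, 3.0.3 plans latent classes, and the two practice-level factors cannot be contrasted within sites at all.

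Finally, the aim is exploratory. That limits the consequence, though not the case for a correction this cheap.

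**Conclusion.** The point holds as a minor analysis-choice issue. If 3.1.1 is run as written, one pooled variance is applied to a binary outcome, and subgroup bounds can be too narrow or too wide when subgroups differ in size and in p(1-p). The standard-error error is capped at a factor of 1.25 (or 0.80) by the SAP's range. It is about 12% in the assumed illustration, about 2% or less at 40 to 60% completion, and nil for the interaction when subgroups are of equal size. The sizes rest on assumed shares and rates, a 95% base level, and the command's default variance being used. The main randomised comparison in SAP 2.1 is not affected.

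**What to change.** - In 3.1.1, keep the model and its point estimates, and state a robust variance: heteroskedasticity-consistent, or clustered by site to match 3.2.
- In 3.1.2, give the family and link, and use the same variance. A Gaussian choice would otherwise share the problem.
- State which of the two models supplies the reported Bonferroni bounds, and for how many contrasts, and build those bounds from the robust standard errors.

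The cost is one code option and a few SAP sentences. The 3.1.1 point estimates do not change. There is a small downside: robust errors can under-cover slightly for very small subgroups (94.2% heteroskedasticity-robust and 93.4% clustered in the 10% minority simulation, still better than 92.0%).

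The stratified Mantel-Haenszel risk difference in 2.1.2.2 is not an interchangeable substitute. It weights strata differently, so the point estimates would generally change, and a 10% subgroup at 44 children per site leaves only about four minority children per site.
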